Statistical Analysis Plan: The volumetric and linear data obtained from the CBCT scans will be analyzed using the same test utilized for the histomorphometric data analyses, setting the significance level at 0.05. The Bonferroni method for correction will be applied and the false positive rate will be calculated. Wound Healing Index (WHI) values obtained will be analyzed using the Kruskal-Wallis test. The null hypothesis states that no differences in WHI will be found at different time points. Likewise, the self-reported level of discomfort and PROMs will be compared using the Kruskal-Wallis test. The level of discomfort and the post-op visits will be the dependent and independent variable respectively. The significance level will be set at 0.05. Other clinical variables recorded in this study will be presented using descriptive statistics (i.e., ITVs, marginal bone levels, and peri-implant mucosal outcomes). Nonetheless, the data will be assessed upon collection and suitability of appropriate analyses will be determined upon data distribution.

The specific variables that will be analyzed are as follows:

- Ability to place and provisionalize the implant following a completely digital protocol (e.g., Azentro)
- Modified Wound Healing Scale
- PROM data on post-surgical discomfort
- Satisfaction with temporary crown and gum tissue
- Stability of implant during osseointegration healing phase
- Ability to use Azentro digital file to fabricate definitive implant crown prosthesis
- Patient-reported outcome measures of satisfaction collected at 2-week, 6-week, Final Crown Delivery, 1-Year Visit)
- Clinical measure of peri-implant inflammation (probing depths, bleeding upon probing, keratinized gingiva, gingival index, plaque index)

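### The SAP leaves the final choice of test until after data collection with no operating rule, and the test it names does not suit repeated visits, so the stated 0.05 level is not guaranteed

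*Combined protocol and SAP*

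**What the plan says.** All of this is in the paragraph headed Statistical Analysis Plan of the combined document.

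- **WHI:** "Wound Healing Index (WHI) values obtained will be analyzed using the Kruskal-Wallis test". The comparison is across visits: "The null hypothesis states that no differences in WHI will be found at different time points".
- **Discomfort and PROMs:** "the self-reported level of discomfort and PROMs will be compared using the Kruskal-Wallis test", with post-operative visit as the independent variable. "The significance level will be set at 0.05".
- **CBCT volumes and distances:** these "will be analyzed using the same test utilized for the histomorphometric data analyses, setting the significance level at 0.05". The document describes no histomorphometric analysis, so no test is identified. A Bonferroni correction follows, without the number of tests in the family.
- **Other clinical variables** (including marginal bone levels) are to be described, not tested.
- **The closing sentence:** nonetheless, "the data will be assessed upon collection and suitability of appropriate analyses will be determined upon data distribution".

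The Design paragraph describes a single cohort, so comparisons between visits are within patients. The variable list gives four collection times for the satisfaction PROMs: 2 weeks, 6 weeks, final crown delivery and 1 year.

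**The concern.** A 0.05 level describes a procedure fixed before the results are known. Here the plan names a test and then leaves its suitability to be judged once the data are in. It gives a basis, the distribution of the data, but nothing that makes the basis operate: no diagnostic, no cut-off, no replacement test, no list of outcomes covered, and no statement that the choice precedes sight of the results. Two analysts following this text could report different p-values, and a reader could not tell a planned result from a selected one.

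The clause is also likely to be used. Kruskal-Wallis assumes independent groups, and these visits are repeated measurements on the same people. A careful analyst would have good reason to leave the named test, and the closing sentence is the only guidance on what comes next. For CBCT the choice is open from the start.

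**Working it through.** **Inputs.** From the document: level 0.05, Kruskal-Wallis for WHI, discomfort and PROMs, one cohort, four visits (stated for satisfaction PROMs only). Assumed, because the document is silent: 15 or 30 patients, equal correlation r between visits, and normal, log-normal or ordinal scores. The 0.05 is a chosen nominal level, so there is no derived figure to reproduce.

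**Step 1: the named test on repeated visits.** With correlation r, visit means vary around each other with variance (1 − r)σ²/n, while an independent-groups test expects σ²/n. With 4 visits the Kruskal-Wallis statistic therefore behaves roughly as (1 − r) times a chi-square on 3 degrees of freedom (critical value 7.815). The true rejection rate is about P(χ²₃ > 7.815/(1 − r)):

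| r | 7.815/(1 − r) | Approximate rate | Simulated rate |
|---|---|---|---|
| 0 | 7.815 | 5.0% | 4.7% to 5.3% |
| 0.3 | 11.16 | 1.1% | 0.9% to 1.5% |
| 0.5 | 15.63 | 0.1% | 0.1% to 0.7% |
| 0.6 | 19.54 | 0.02% | 0.0% to 0.3% |

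The simulation reproduces 0.05 when visits are independent, which checks the code. It misses 0.05 on the low side once visits are correlated.

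**Step 2: leaving the choice open.** Rejection rates with no true change, from simulations of 4,000 data sets per scenario (Monte Carlo standard error near 5%: √(0.05 × 0.95/4000) = 0.34 percentage points):

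| How the test is chosen | r = 0, 0.3, 0.6 | r = 0.5 |
|---|---|---|
| Friedman, fixed in advance | 4.0% to 5.3% | 4.3% to 5.5% |
| Shapiro-Wilk check picks Friedman or repeated-measures ANOVA | 4.0% to 5.4% | about 4% to 6% |
| Smaller p-value of Friedman and repeated-measures ANOVA | 5.6% to 8.2% | about 6% to 8% |

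A disciplined distribution rule roughly keeps the level. Picking the better of two within-patient tests does not.

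**Step 3: starting from the named test.** At r = 0.5, the smaller p-value of Kruskal-Wallis and Friedman rejects about 5%, and that of Kruskal-Wallis and repeated-measures ANOVA about 3% to 6%. Replacing the named test by a single within-patient test does not inflate the error. Inflation arises when two such tests are run and one is kept.

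**Step 4: what Kruskal-Wallis costs.** For an assumed steady shift totalling 0.5 SD from first to fourth visit, r = 0.5, power is about 6% (Kruskal-Wallis) against 25% (Friedman) with 15 patients, and 20% against 52% with 30.

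**The case against.** The strongest reply is that the sentence describes a choice made on distribution, and such a choice does no harm (Step 2, second row). Inflation needs an analyst to run two tests, neither named in the SAP, and keep the smaller p-value. The text does not say anyone will do that. This stands, and it limits the claim to a level that is not guaranteed. It does not supply the missing rule: nothing in the document separates the harmless use from the harmful one. Bonferroni does not either, since it adjusts for the number of tests and not for choosing among candidate tests of one outcome.

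Three stronger readings are tempting but unsupported:

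- **A larger error rate.** If the analyst could also switch to a first-versus-last visit comparison, simulation gives about 9% to 12%. The sentence ties the choice to distribution. Changing the visit contrast changes the hypothesis, which the SAP states across time points, so this figure should not be used.
- **That every planned analysis is cancelled.** The sentence directly follows the one on descriptive variables and could be confined to them. The wording is unrestricted, so the wider reading is more natural, but scope is unstated. On the narrow reading it would let tests be added to outcomes planned as descriptive. For CBCT no named test exists to be overridden.
- **That the analyst works with visit labels in view.** The document says nothing about this either way.

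**Conclusion.** The point holds in limited form. The SAP names one test for three groups of outcomes, leaves the CBCT test unidentified, and defers the final choice to a distribution assessment with no operating rule. The true error rate then depends on conduct that the plan does not fix: under 1% if Kruskal-Wallis is kept, about 4% to 6% under an honest distribution rule, and about 6% to 8% if the better of two within-patient tests is taken. These figures rest on 15 to 30 patients, 4 visits, correlation 0.5 and the score distributions tried. Serious inflation has not been shown.

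The missing rule alone would be close to a request for detail. It deserves action because it is tied to an unsuitable named test, whose cost in power is larger than the possible inflation, and one revision settles both.

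**What to change.** Revise the Statistical Analysis Plan paragraph as follows.

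1. **WHI, discomfort, PROMs:** replace Kruskal-Wallis with a Friedman test across visits, followed by Wilcoxon signed-rank tests for visit pairs listed in advance. List the visits for each outcome.
2. **Missing visits:** Friedman uses only patients with every visit. State how a patient with a missing visit is handled, and report how many are affected.
3. **CBCT measures:** specify the within-patient change with a 95% CI and one named paired test. Keep the stated Bonferroni correction and give the number of tests it covers.
4. **Marginal bone levels:** leave as descriptive, as planned.
5. **Closing sentence:** replace it with a statement that any analysis prompted by the data distribution is reported beside the planned one as sensitivity and does not replace it. Do not simply delete it, since that would fix Kruskal-Wallis in place.

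The cost is SAP wording only; no data collection changes. There are two statistical downsides. Signed-rank tests assume symmetric differences under the null. Friedman gives up some power to repeated-measures ANOVA when scores are normal: in a check of the Step 4 scenario with 3,000 data sets per case, about 27% against 35% with 15 patients and 52% against 65% with 30. With log-normal scores the order reversed (26% against 17%, and 52% against 37%).

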- Official Title: CLINICAL, RADIOGRAPHIC, AND HISTOMORPHOMETRIC ANALYSIS OF ASTRA TECH IMPLANT EV PLACED AND IMMEDIATELY PROVISIONALIZED INTO PRESERVED ALVEOLAR RIDGES: A PROSPECTIVE 3-YEAR OUTCOMES STUDY
- NCT Number: NCT04255342
- Document Date: August 9, 2024

Objective: The objective of this study is to compare and evaluate the stability of the implant body, survival rate, bone-level changes, and the implant's soft-tissue outcomes over a period of 1 year.

Design: This study is a cohort study (*ClinicalTrials.gov identifier- NCT04255342*). The study population consists of adults aged 18-95 years old who are seeking care at the University of Iowa, College of Dentistry and Dental Clinics. Eligibility for the study included needing an implant placement and final crown delivery at the site of a single-rooted tooth that had previously undergone tooth extraction with bone grafting.

Methods: At least 3 months after tooth removal and bone grafting, consented subjects will undergo implant placement and immediate loading with a temporary crown. More specifically, a dental implant will be placed using Azentro, a commercially-available product that uses computer technology to plan the dental implant placement using the AstraTech Implant System EV and an immediate implant temporary crown will be placed using Azentro. After 3-months, a definitive all-ceramic crown will be placed that was made using a digital workflow. Participants will have a 1-year follow-up visit after placement of the definitive all-ceramic crown, specifically for data collection.

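### Satisfaction at crown delivery and at 1 year comes only from definitive-crown recipients, and the planned unpaired test ignores both this and the repeated ratings

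*Combined protocol and SAP*

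**What the plan says.** The SAP's closing variable list gives four satisfaction time points: "Patient-reported outcome measures of satisfaction collected at 2-week, 6-week, Final Crown Delivery, 1-Year Visit".

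The Methods paragraph fixes what the last two require. On the crown: "After 3-months, a definitive all-ceramic crown will be placed that was made using a digital workflow". On the final visit: "Participants will have a 1-year follow-up visit after placement of the definitive all-ceramic crown, specifically for data collection". The 1-year visit is therefore timed from the definitive crown, not from implant surgery.

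On the test, the SAP paragraph says: "Likewise, the self-reported level of discomfort and PROMs will be compared using the Kruskal-Wallis test". The sentence before it concerns a wound-healing comparison across time points. The sentence after it reads: "The level of discomfort and the post-op visits will be the dependent and independent variable respectively". The level is given as: "The significance level will be set at 0.05".

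The Objective includes "stability of the implant body, survival rate, bone-level changes, and the implant's soft-tissue outcomes over a period of 1 year", so implant loss is foreseen. The variable list also treats as an outcome whether the digital file can be used to make the definitive crown. No failure rate, sample size or satisfaction scale is given. The SAP states no analysis set for satisfaction, no handling of patients who do not reach the crown, and no within-patient comparison.

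**The concern.** A patient who loses the implant, or for another reason never receives the definitive crown, can supply 2-week and 6-week ratings but, as the visits are defined, not the later two. The set of patients behind the summary therefore changes between the second and third rating, and it changes according to an outcome of the study itself.

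Kruskal-Wallis takes whatever ratings exist at each visit as that visit's group and never compares a patient with himself or herself. Two things follow:

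- A change in who is rated can look like a change in satisfaction.
- The correlation between one patient's ratings is ignored, so the test is not valid in the usual sense for repeated data. Here it errs on the conservative side and can miss real change.

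At stake is the reading of the satisfaction trend and of the 1-year level, which a reader may take to describe everyone treated.

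**Working it through.** The plan gives no figure to reproduce. Every rate and score below is an assumption, shown over a range.

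**1. Shift in the visit mean when no patient changes.** Let f be the fraction never reaching the crown, mC the mean score of those who reach it and mN the mean of those who do not.

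- Mean at 2 and 6 weeks, if all are rated: (1 - f) x mC + f x mN
- Mean at crown delivery and 1 year: mC
- Apparent rise: mC - [(1 - f) x mC + f x mN] = f x (mC - mN)

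On a 0-10 scale: 0.03 x 2 = 0.06 points; 0.10 x 4.5 = 0.45 points.

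On a 0-100 scale, take 20 patients, 18 scoring 90 and 2 scoring 40 at every visit attended. Early mean = (18 x 90 + 2 x 40)/20 = 85. Late mean = 90. The rise is 5 points, which equals 0.10 x 50.

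With mC = mN the expected rise is 0.

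**2. What the planned test does with this.** The four-visit Kruskal-Wallis test at 0.05 was simulated with 1500 runs per setting. Each patient's score was identical at all visits attended (assumed SD 12 on a 0-100 scale). Patients not reaching the crown were 0 to 3 SD less satisfied.

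| N | Fraction lost | Gap (SD) | Mean rise (SD) | Runs with p < 0.05 |
|---|---|---|---|---|
| 20, 40, 100 | 5% | 1 to 3 | 0.05 to 0.15 | 0% |
| 20, 40, 100 | 10% | 1 to 3 | 0.10 to 0.30 | 0% |
| 20, 40 | 20% | 1 to 3 | 0.2 to 0.6 | 0% |
| 100 | 20% | 2 | 0.40 | 46% |
| 100 | 20% | 3 | 0.60 | 99.9% |
| 40 | 30% | 2 | 0.59 | 13% |
| 40 | 30% | 3 | 0.89 | 82% |

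For losses of 5% to 20% and gaps of 1 to 3 SD, the visit mean rose in 83% to 100% of runs. With no gap it rose in about half the runs, and by 0 on average. The 0-10 case with 10% lost and a gap of 4.5 (assumed SD 1.2) also gave 0% rejections at N = 20, 40 and 100.

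**3. What the unpaired test costs.** Assume four ratings per patient, within-patient correlation 0.7 and N = 40. With no true change, Kruskal-Wallis rejects in about 0% of runs and Friedman in about 5%, its nominal level. With a true change of 0.4 SD, power is about 38% for Kruskal-Wallis and 94% for Friedman. The exact values depend on which visits the change falls between.

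**4. After the fix.** In step 1 each patient's own change is 0 by construction. A within-patient comparison therefore shows a rise of exactly 0 at every f and every gap.

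**The case against.** The strongest counter-argument is that the planned test does not react to this mechanism at realistic sizes. That stands: step 2 shows no rejections at losses of 10% or less. A reader might infer that the plan is likely to produce a falsely significant improvement. In these simulations that happened only with losses of 20% to 30% and, mostly, large gaps, and the documents give no reason to expect either.

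A reader might also infer that the least satisfied patients leave and that results are therefore biased in favour of the procedure. The documents do not say so. A patient whose implant fails after week 6 may have rated normally at 2 and 6 weeks, and then the visit mean does not shift on average. The direction is plausible but assumed.

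Nor do the documents say that every treated patient is rated at 2 and 6 weeks, or that the 1-year ratings come from successes only. An early failure might miss an early rating. A patient who loses the implant after crown delivery could still attend at 1 year, and a replaced implant could be crowned later. What the text supports is dependence on having received the definitive crown.

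Visit is the explicit grouping variable for discomfort, and it reaches satisfaction only through the sentence linking the patient-reported outcomes to the preceding comparison. It is also not stated that one common item is used at all four visits; satisfaction with the temporary crown and gum tissue is listed separately. This is a natural reading rather than an explicit statement, and the SAP should settle it.

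The SAP's clause letting the choice of analysis follow the data does not answer the point. It concerns distribution, not who contributes at each visit or whether ratings are paired.

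**Conclusion.** The concern holds in limited form. As written, the last two satisfaction ratings require the definitive crown, the first two do not, and the planned test treats the visits as independent groups.

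If patients who never reach the crown were already less satisfied early, visit summaries rise by f x gap without any patient changing: 0.06 to 0.45 points on a 0-10 scale under the assumptions in step 1. At 10% loss or less this shows in the descriptive pattern and not in the p-value.

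The choice of an unpaired test for repeated ratings is a fault whatever the failure rate. Under the assumptions in step 3 its main effect is lost power. The actual size of either effect cannot be fixed from the documents. Satisfaction is not named in the Objective, so this is a modest but worthwhile correction.

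**What to change.** - **Test.** Replace Kruskal-Wallis for satisfaction across visits with a within-patient analysis. Use a Friedman test in patients with all four ratings, or paired signed-rank tests in patients rated at both visits compared, with a stated multiplicity correction. For example, three comparisons against week 2 under Bonferroni use 0.05/3 = 0.0167 each. State which satisfaction item is common to the visits compared.
- **Reporting.** Beside each visit give the number rated and the number who did not reach the definitive crown. Label the crown-delivery and 1-year results as describing crown recipients.
- **Optional.** As a sensitivity analysis, analyse all treated patients with failures counted as not satisfied. It answers a different question and mixes implant survival, already a separate objective, into satisfaction, so it should not replace the main result. For scale: if an assumed 90% of crown recipients are satisfied and 5% never reach the crown, it gives 0.90 x 0.95 = 85.5%.

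The cost is a few lines of SAP text and no new data. The downside is that the paired set may be slightly smaller than the set of all ratings.

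### The four satisfaction ratings span the change of crown and come from the same patients, but the natural reading of the SAP compares them with one Kruskal-Wallis test, which ignores the pairing and does not locate a change

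*Combined protocol and SAP*

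**What the plan says.** **Crown sequence (Methods).** At surgery, "consented subjects will undergo implant placement and immediate loading with a temporary crown". Later, "After 3-months, a definitive all-ceramic crown will be placed". The last visit is 1 year after the definitive crown. The Design paragraph calls this a cohort study, and no comparison arm is described.

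**Ratings (variable list in the Statistical Analysis Plan).** One item is "Patient-reported outcome measures of satisfaction collected at 2-week, 6-week, Final Crown Delivery, 1-Year Visit". A separate item is "Satisfaction with temporary crown and gum tissue". The list does not say what the four-visit item rates, or whether the delivery-visit rating comes before or after the crown is changed.

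**Test (Statistical Analysis Plan).** For the Wound Healing Index, "The null hypothesis states that no differences in WHI will be found at different time points". The text continues: "Likewise, the self-reported level of discomfort and PROMs will be compared using the Kruskal-Wallis test". The grouping factor is then written out for discomfort only: "The level of discomfort and the post-op visits will be the dependent and independent variable respectively". For patient-reported outcomes the plan names no crown factor, no contrast between visits and no method for repeated measures. The paragraph closes by leaving the choice of analysis open until the data distribution has been seen.

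**The concern.** Two things are wrong with a single Kruskal-Wallis test here.

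First, it is a test for independent groups. Each patient contributes up to four ratings, and a patient who rates high at one visit will tend to rate high at the others. The test leaves that between-patient spread in its yardstick, so it is too cautious and misses changes that the data could show.

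Second, the four visits are not a plain time series, because the crown in the mouth changes part-way. A significant result would say only that at least one visit differs. It would not say whether satisfaction drifted while the temporary crown was worn, drifted after the definitive crown was fitted, or moved when one replaced the other. Those are different messages for a study of a digital workflow that makes both crowns.

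**Working it through.** The documents give no sample size, effect size, SD, correlation or rating scale, so there is no figure of the plan's own to reproduce. All simulation inputs are assumptions: 15, 20 or 30 patients; four normally distributed ratings with SD 1; within-patient correlation r = 0 or 0.5; significance level 0.05, as in the SAP. There were 3,000 or 4,000 runs per setting. Real scores may be ordinal with ties, so the figures show direction and rough size only.

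**1. Can crown and visit be separated?** A model with an intercept, three visit indicators and one crown indicator has 1 + 3 + 1 = 5 columns. If delivery is rated after the change, the crown column equals the delivery indicator plus the 1-year indicator. If it is rated before, the crown column equals the 1-year indicator. Either way the rank is 4, so a crown effect cannot be estimated alongside free visit effects. Replacing the visit indicators with a straight line in time makes the crown term estimable, but only through the assumed shape of the time trend.

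**2. Does the omnibus test distinguish the two explanations?** A pure crown step of 0.8 SD was compared with a pure log-time trend with the same variance of visit means (visits at about weeks 2, 6, 13 and 65). Kruskal-Wallis rejection rates at r = 0.5:

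| n | crown step | time trend |
|---|---|---|
| 15 | 0.66 | 0.66 |
| 20 | 0.85 | 0.84 |
| 30 | 0.98 | 0.98 |

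The test responds equally to both.

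**3. What does ignoring the pairing do?** Differences between visits vary in proportion to 1 − r, but Kruskal-Wallis judges them against the full spread. At r = 0.5 its statistic is shrunk by roughly 1 − 0.5 = 0.5, while the critical value stays the same. Rejection rates when nothing changes:

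| n | Kruskal-Wallis, r = 0 | Kruskal-Wallis, r = 0.5 | Friedman, r = 0.5 |
|---|---|---|---|
| 15 | 0.048 | 0.003 | 0.044 |
| 20 | 0.043 | 0.004 | 0.046 |
| 30 | 0.048 | 0.003 | 0.045 |

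Across repeat simulations the Kruskal-Wallis figure at r = 0.5 was about 0.003 to 0.005.

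**4. What does each analysis detect?** With n = 20 and r = 0.5, a pure step at the crown change gives:

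| Shift | Delivery rated | Kruskal-Wallis | Friedman | Switch contrast, unadjusted | Switch contrast, Holm over three |
|---|---|---|---|---|---|
| 0.5 SD | after change | 0.28 | 0.60 | 0.54 | about 0.35 |
| 0.5 SD | before change | 0.17 | 0.47 | 0.54 | about 0.35 |
| 0.8 SD | after change | 0.85 | 0.96 | 0.90 | about 0.80 |

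Repeat runs put the unadjusted contrast at 0.5 SD at about 0.55. The gap between Kruskal-Wallis and the unadjusted contrast is mostly the pairing. With delivery rated after the change, Friedman on the same four visits exceeds the contrast (0.60 against 0.54). With delivery rated before it, Friedman recovers (0.473 − 0.171) / (0.539 − 0.171) = 0.302 / 0.368, about 82% of the gap.

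**The case against.** Five points can be made for the plan.

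- **The SAP never states that satisfaction is tested across visits.** True: visit is named as the factor for discomfort only. But Kruskal-Wallis needs a grouping factor, no arm is described, and satisfaction is listed by visit. If visit is not meant, the SAP gives no factor for this outcome, and that also needs stating.
- **The item may not rate the crown.** This stands. If it rates overall care, the rated object does not change, although the visits still span the crown change and the ratings are still paired.
- **The closing sentence leaves the method open.** It ties the choice to distribution. A distribution shows neither that ratings are paired nor which crown was rated at delivery.
- **The plan never claims that a difference would be due to time.** This stands. A test of differences between visits is a legitimate question; what is limited is its interpretation.
- **Adjusted contrasts may do worse than the planned test.** This stands in part. At 0.8 SD with delivery rated after the change, the Holm-adjusted switch contrast (about 0.80) falls below Kruskal-Wallis (0.85).

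A reader might also infer that the study cannot report satisfaction with each crown. The documents do not support that: scores exist by visit, and satisfaction with the temporary crown is its own listed item. Nor does the low power of Kruskal-Wallis come mainly from combining two crowns in one test; step 4 of the working shows that most of it comes from ignoring the pairing.

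**Conclusion.** The point holds in a limited form. The satisfaction visits span the crown change, and the natural reading is one independent-groups test on repeated ratings. At an assumed correlation of 0.5, that test rejects about 0.003 to 0.005 of the time under no change instead of 0.05. At a 0.5 SD step in 20 patients it detects 0.28 or 0.17, against 0.60 or 0.47 for Friedman on the same data. Its p-value also cannot place a change within or across crowns.

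The error is towards missing changes, not towards false positives. It would be tempting to say that a better test could isolate a crown effect. It could not: every patient changes crown at the same stage and there is no comparison group, so the limit lies in the design. What the SAP can gain is a valid repeated-measures test and a clear reading within each crown. Because satisfaction is outside the stated objective, this is a minor to moderate point. The sizes rest on assumed n, correlation, shift and normal scores; the pairing and the aliasing do not.

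**What to change.** Replace the Kruskal-Wallis test for satisfaction in the Statistical Analysis Plan with the following.

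1. **Overall test.** Friedman over the four visits, on patients with all four ratings; a mixed ordinal model with a patient effect if ratings are missing.
2. **Three prespecified paired contrasts**, each a Wilcoxon signed-rank test with a Hodges-Lehmann 95% confidence interval, Holm-adjusted and reported whatever the overall result:
   - 2 versus 6 weeks (temporary crown);
   - delivery versus 1 year (definitive crown, if delivery is rated after the change);
   - 6 weeks versus the first rating of the definitive crown, reported as crown plus elapsed time and not as a crown effect alone.
3. **Definitions.** State what the four-visit item rates and, on the delivery-visit form, which crown is meant. If it is the temporary crown, group that rating with 2 and 6 weeks, so that the second contrast becomes 6 weeks versus delivery, and use 1 year for the last contrast.

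The cost is SAP wording and one line on a form. The statistical price is the Holm adjustment: under the assumptions above (20 patients, 0.5 SD, correlation 0.5), power for the switch contrast falls from about 0.55 to about 0.35. Friedman also drops patients with an incomplete set of ratings, which is why the mixed model is named. Full separation of crown from time would need a comparison group and is not offered by this change.
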